#### **8.4.8 Medical Device Deficiencies**

Medical devices approved for use with Jivi are being provided for use in this study to facilitate the preparation and infusion of the study intervention. To fulfill regulatory reporting obligations worldwide, the investigator is responsible for the detection and documentation of events meeting the definitions of device deficiency that occur during the study with such devices.

The definition of a medical device deficiency can be found in [Section 11.5.3](#).

Device deficiencies only should be reported to the sponsor, by completing the Product Technical Complaint form and submitting it to the sponsor via the email address ([contact]) given to the site.

NOTE: Deficiencies fulfilling the definition of an AE/SAE will follow the processes outlined in [Section 11.5.5](#) of the protocol.

#### **8.5 Pharmacokinetics**

##### **8.5.1 Incremental Recovery and Trough Levels of Jivi**

Blood samples for Jivi incremental recovery, FVIII levels, and FVIII trough levels will be collected in all participants. Incremental recovery will be determined at Baseline (Day 1) by collecting a sample for FVIII level before the scheduled infusion and a second sample collected 15 to 30 minutes after end of the infusion. A third sample collected at a minimum of 4 hours after the end of the infusion to assess FVIII levels. The measurements should only be performed when the participant is not actively bleeding. If a participant is actively bleeding, the samples for incremental recovery will be postponed until the sample can be done after a prophylactic dose.

The exact sampling times before and after infusion and the dose administered will be documented in the CRF. Incremental recovery of Jivi is determined by measuring FVIII activity with a validated assay for FVIII.

Infusions given at study visits will be recorded in the site participant records, which will be the source documents and will be used to enter this information in the CRF.

All samples will be processed in the investigator's local laboratory. Plasma concentrations of FVIII will be measured using a validated FVIII activity assay.

Recoveries should be performed using the participants assigned treatment dose, rounded to full vial size.

At Month 3 (72 hours after the previous infusion), FVIII levels will be measured for all participants for the WAPPS-Hemo PK analysis. For participants on the twice weekly regimen, this will also serve as 1 of 2 trough level measurements (i.e. Day 3 of 2x/week regimen). At Month 6 [EOS]), samples for trough levels will be collected just prior to the scheduled infusion for all participants in alignment with the prophylaxis regimen (i.e. at Day 4 for 2x/week regimen, at Day 5 for Q5D regimen, and at Day 7 for less frequent regimens).

### **8.5.2 Web-Accessible Population Pharmacokinetic Service-Hemophilia (WAPPS-Hemo) Analysis**

The WAPPS-Hemo database will be used to assess sources of variability between participants' PK data and clinical risk scores. WAPPS-Hemo is a centralized, dedicated, actively moderated database run by the Health Information Research Unit at McMaster University that allows participating hemophilia treatment sites to input FVIII data from sparse samples and receive individual PK estimates. These estimates are generated by an automated proprietary population PK engine and are then manually validated.

The WAPPS-Hemo analysis will be performed at the end of Visit 5 (Month 3). Each study site investigator will register in WAPPS-Hemo database

(<https://www.wapps-hemo.org/UserRegistration.aspx>), if not already registered. Once a site is registered, the investigator will enter the required participant details (gender, date of birth, baseline factor level, blood group, and positive history of inhibitors). The investigator will then enter infusion data at least 3 time points post-infusion (with or without pre-infusion levels), as specified in the SoA (Section 1.3). The investigator will be required to input the following data for each infusion: weight, height, dose and type of factor administered (as total and IU/kg), and infusion duration. If available, hematocrit, hemoglobin, serum creatinine, vWF measurements, and laboratory methods used to measure FVIII will also be entered.

Data entered will be cleaned by WAPPS-Hemo PK experts. Duplicate submissions will be removed, and all original data that was duplicated from merged infusions will be deleted. Any data not valid for modelling, such as user input errors, insufficient data, or conditions that exclude use of participant data will be removed and excluded from analysis. The dataset will be analyzed to search for outliers. Input errors missed at the source will be corrected where the incorrect measurement has been used (i.e. weight, height).

The investigator will then request extraction of the following from the database: predicted post-infusion measurement of plasma factor activity level on Day 0 (Day of Infusion) up to Day 8, estimated terminal half-life, and time to 0.01, 0.02, 0.05, 0.1, and 0.2 IU/mL (with their credibility intervals), FVIII trough level (2 measures for participants with 2x/week regimen), AUC, clearance, and predicted peak factor value. Once extracted, the data will be stored in the participant's medical record and entered into the electronic CRF.

## 8.6 Pharmacodynamics

Pharmacodynamics parameters are not evaluated in this study.

## 8.7 Genetics

Genetics parameters are not evaluated in this study.

## 8.8 Biomarkers

Biomarkers are not evaluated in this study.

## 8.9 Other Investigations

Investigations related to the mode of action or the safety of Jivi and similar drugs may be performed. The same applies to further investigations deemed relevant to hematologic diseases and associated health problems. Examples of these investigations include diagnostic, safety, pharmacodynamics, monitoring, or potentially predictive biomarkers.

Results from any additional investigations may be reported separately.

## 8.10 Medical Resource Utilization and Health Economics

Medical Resource Utilization and Health Economics data, associated with medical encounters, will be collected by the investigator and study site personnel for all participants throughout the study. Protocol-mandated procedures, tests, and encounters are excluded.

The data collected may be used to conduct exploratory economic analyses and will include:

- Number and duration of medical care encounters, including surgeries, and other selected procedures (inpatient and outpatient)
- Duration of hospitalization (total days or length of stay, including duration by wards [e.g. intensive care unit])
- Number and type of diagnostic and therapeutic tests and procedures
- Outpatient medical encounters and interventions (including physician or emergency room visits, tests and procedures, and medications).

## 9. Statistical Considerations

### 9.1 Statistical Hypotheses

The study is not designed to test any predefined hypothesis. All analyses will be descriptive or exploratory.

### 9.2 Sample Size Determination

The primary endpoint is the occurrence of favorable outcome on the score selected dosing regimen, which will be described via the proportion of participants with a favorable outcome.

The target sample size for this study is based on feasibility. It is expected that a minimum of 20-25 participants will be enrolled. The precisions, in terms of the width of the 95% confidence intervals (CIs), for different sample sizes and proportions of participants with a favorable outcome are shown in [Table 9-1](#).

**Table 9–1: Expected Precision of Estimates by Sample Size and Assumed Proportion of Participants with Favorable Outcome**

N	Assumed true proportion of participants with favorable outcome	Expected observed proportion of participants with favorable outcome	95% CI, %	Width of CI, %
15	65%	9/15 = 60%	[32.3; 83.7]	51.4
	70%	10/15 = 67%	[38.4; 88.2]	49.8
	75%	11/15 = 73%	[44.9; 92.2]	47.3
	80%	12/15 = 80%	[51.9; 95.7]	43.8
	85%	12/15 = 80%	[51.9; 95.7]	43.8
	90%	13/15 = 87%	[59.5; 98.3]	38.8
20	65%	13/20 = 65%	[40.8; 84.6]	43.8
	70%	14/20 = 70%	[45.7; 88.1]	42.4
	75%	15/20 = 75%	[50.9; 91.3]	40.4
	80%	16/20 = 80%	[56.3; 94.3]	37.9
	85%	17/20 = 85%	[62.1; 96.8]	34.7
	90%	18/20 = 90%	[68.3; 98.8]	30.5
25	65%	16/25 = 64%	[42.5; 82.0]	39.5
	70%	17/25 = 68%	[46.5; 85.1]	38.6
	75%	18/25 = 72%	[50.6; 87.9]	37.3
	80%	20/25 = 80%	[59.3; 93.2]	33.9
	85%	21/25 = 84%	[63.9; 95.5]	31.5
	90%	22/25 = 88%	[68.8; 97.5]	28.7
30	65%	19/30 = 63%	[43.9; 80.1]	36.2
	70%	21/30 = 70%	[50.6; 85.3]	34.7
	75%	22/30 = 73%	[54.1; 87.7]	33.6
	80%	24/30 = 80%	[61.4; 92.3]	30.9
	85%	25/30 = 83%	[65.3; 94.4]	29.1
	90%	27/30 = 90%	[73.5; 97.9]	24.4

Abbreviation: CI = confidence interval.

Exact Clopper-Pearson 95% CIs were calculated.

When 70% of participants with favorable outcome are observed, a sample size of 20 participants will produce a two-sided 95% CI with a width of 42.4% (95% CI = 45.7% to 88.1%). It is acknowledged that the precision of estimates will be low for the anticipated sample size range. This will be considered in the interpretation of results. While it may not be possible to draw any conclusions based on the reduced sample size, the study may provide first hints whether the score could be useful in clinical practice.

### 9.3 Analysis Set

For the purposes of analysis, the following analysis sets are defined in [Table 9–2](#):

**Table 9–2: Analysis Sets**

Participant Analysis Set	Description
Enrolled	All participants who signed the ICF
Modified intention-to-treat (mITT) set	All enrolled participants who had received at least 1 dose of study intervention, who have infusions/bleeding data from the diary and CRF available, and who have been followed for a minimum of 4 months
Safety analysis set	All participants who had received at least 1 dose of study intervention

Abbreviations: CRF = case report form; ICF = informed consent form.

## 9.4 Statistical Analyses

The SAP will be finalized prior to before first participant first visit (FPFV) and will include a more technical and detailed description of the statistical analyses described in this section. This section is a summary of the planned statistical analyses of the most important endpoints including primary and key secondary endpoints.

### 9.4.1 General Considerations

Statistical analyses will be performed using SAS release 9.2 or higher (SAS Institute Inc., Cary, North Carolina, United States [US]). The version used will be specified in the SAP.

All variables will be analyzed descriptively with appropriate statistical methods: categorical variables by frequency tables (absolute and relative frequencies) and continuous variables by sample statistics (i.e. mean, standard deviation [SD], minimum, median, quartiles, and maximum). Continuous variables will be described by absolute value and as change from baseline per analysis time point, if applicable.

All endpoints will be analyzed according to the modified intention-to-treat (mITT). The entire study period will be analyzed regardless of the regimen.

Some tables will be stratified by the risk score-selected dosing regimen. Additionally, some selected tables (including the primary endpoint, safety events, study intervention administration, prophylaxis regimen, and PK parameters) will be presented in total and by subgroup of history of FVIII inhibitors for sensitivity purposes.

In general, missing clinical outcomes collected in this study will not be imputed. Missing exposure and AE/concomitant medication start/end date will be imputed based on a worst-case scenario.

Baseline is defined as time point of enrollment into study. The participant total risk score will be calculated at baseline and the resulting prophylaxis regimen will be assigned as describe in [Section 4.1](#).

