### 8.3.1 Measurements of Immunogenicity

All participants will be tested for inhibitors to FVIII according to the Bethesda assay as per local clinical practice. A positive inhibitor test is defined with a threshold of  $\geq 0.6$  BU/mL. Repeat testing should be obtained within 1 to 2 weeks of initial identification of a positive result. Only after confirmation of a second positive result does the inhibitor have to be reported as a SAE.

A low post-infusion FVIII level in the absence of detectable FVIII inhibitors indicates that loss of drug effect is likely due to anti-PEG antibodies. Jivi should be discontinued and participants switched to a previously effective FVIII product (refer to [Section 8.4.7](#) as this qualifies for an AESI-Loss of Efficacy [LoE]).

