### 4.6.2 Demographics and Other Baseline Characteristics

- Demographic characteristics: Age, sex, race and ethnicity, blood group (ABO, from disease history), height, weight, and BMI at screening, and employment will be presented overall for the safety analysis set and by risk score group.
- Disease history: Type of hemophilia, years since diagnosis, previous treatment with Factor VIII, history of FVIII inhibitors (yes/no), age (years) at first treatment, treatment regimen type(s), treatment regimen changed (from first treatment), type of first treatment, FVIII level at time of diagnosis, type of Factor VIII gene mutation, history of inhibitor, history of target joints, at least one target joint at time of screening, and family history of hemophilia, will be presented overall for the safety analysis set and by risk score group.
- Details of previous or current SHL treatment product and regimen, used for score calculation, within 12 months of Baseline Visit: Start and end period (months prior to date of informed consent), number of bleeding events in the assessment period, bleeding events standardized to last 12 months (ABR, quantitative), number of joint bleeds in the assessment period and standardized to the last 12 months,
- Risk score assessment: Bleed phenotype (ABR category), pre-study treatment frequency, number of active target joints, vWF antigen levels, physical activity level (low, sedentary, medium/high), total risk score, and risk score group will be presented overall for the mITT set and by risk score group.

- Medical history excluding study indication: Medical history will be coded using the latest version of MedDRA. Medical history SOC and PT frequencies will be summarized for the safety analysis set overall.
- Prior/concomitant medications: Medications will be classified using the latest version of WHODRUG. Prior medications and concomitant will be summarized separately by ATC class (Level 1 - Anatomical Main Group) and subclass (Level 2 - Therapeutic Subgroup) for the safety analysis set overall. Separate summaries will be presented of all prior medications, prior medications ongoing at study intervention start date, all concomitant medications and concomitant medications started during the study intervention period.

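### Quantities complete at baseline (the risk score table, the ABO/BMI scores and possibly incremental recovery) are tied to 4 months of later follow-up for a reason that concerns only the ABR

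*Protocol*

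**What the plan says.** **Analysis sets.** Protocol 9.4.1 says "All endpoints will be analyzed according to the modified intention-to-treat (mITT"). Table 9-2 limits the mITT to treated participants with diary and CRF data "and who have been followed for a minimum of 4 months". The safety analysis set has no follow-up condition: "All participants who had received at least 1 dose of study intervention".

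**SAP.** Section 4.1 uses the mITT for effectiveness endpoints and the safety set for safety. Sections 4.4.1 to 4.4.3 (theoretical ABO/BMI scores, WAPPS-Hemo parameters, incremental recovery and troughs) name no set. Section 4.6.2 says of the risk score assessment that "total risk score, and risk score group will be presented overall for the mITT set and by risk score group". Sections 1 and 4.7 declare no departure from the protocol.

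**Baseline characteristics.** Protocol 9.4.5.2 promises these summaries for the mITT and the safety set alike.

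**Timing.** Protocol 8.1.4 takes blood type and BMI at screening, and the risk score is calculated at baseline. For recovery, protocol 8.5.1 says "Incremental recovery will be determined at Baseline (Day 1) by collecting a sample for FVIII level before the scheduled infusion", with a second sample 15 to 30 minutes after the infusion.

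**Low post-infusion levels.** When the level is low and no inhibitor is detectable, protocol 8.3.1 says "Jivi should be discontinued and participants switched to a previously effective FVIII product". Under protocol 7.1, permanent discontinuation ends study participation.

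**The concern.** A 4-month minimum is sensible for a rate that needs observation time. SAP 4.2.2 gives that reason, in its rule for participants who switch regimen early. It does not extend to a blood group, a BMI, a baseline risk score or a recovery measured at the first infusion. Restricting those to participants with 4 months of follow-up selects baseline data on what happened afterwards.

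For the risk score components and the theoretical scores, the cost is usable data lost from a study that expects only 20 to 25 participants and whose subject is the score itself. For incremental recovery the cost could be selective, because a low value is itself a route out of the study. A summary on the mITT could then describe only those whose recovery was good enough to continue.

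**Working it through.** **1. The plan's own precision figure.** Table 9-1 gives 14/20 = 70% with an exact interval of 45.7 to 88.1%. The Clopper-Pearson limits are Beta(0.025; x, n−x+1) and Beta(0.975; x+1, n−x). With x = 14 and n = 20 they are 45.7% and 88.1%, width 42.4. All 24 rows of the table reproduce. The figure concerns the primary endpoint; no precision is stated for the quantities discussed here, so no stated number is contradicted.

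**2. Which set applies to each quantity.**

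| Quantity | Complete at | Pointing to the mITT | Pointing elsewhere | Status |
|---|---|---|---|---|
| Risk score component table | Baseline | SAP 4.6.2, explicitly | Protocol 9.4.5.2: both sets | Firm; SAP departs from the protocol undeclared |
| Theoretical ABO/BMI scores | Baseline | Protocol 9.4.1 | SAP 4.4.1 silent; SAP 4.1 limits the mITT to effectiveness | mITT by literal default |
| Incremental recovery | Day 1 as planned | Protocol 9.4.1 | Protocol 9.4.4.2 places PK under Safety Analyses (Safety Population); SAP 4.4.3 silent | Conflicting |

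**3. Route by which a low recovery could leave the mITT.** Low post-infusion level without inhibitor → Jivi stopped (protocol 8.3.1) → participant does not remain in the study (7.1) → fewer than 4 months of follow-up → outside the mITT (Table 9-2). The third step rests on 7.1. The opening of section 7 instead encourages participants who withdraw from treatment to stay for follow-up, and anyone who did so for 4 months could remain in the mITT.

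**4. Lost precision.** No early-loss rate is given, so a range is assumed: 5, 10, 14.3 and 20%. The 14.3% is 10/70, from the superseded target of 70 enrolled and about 60 evaluable. With N treated and n remaining, the standard error grows by sqrt(N/n).

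| Assumed loss | N = 20: n, ratio | N = 25: n, ratio |
|---|---|---|
| 5% | 19, 1.026 | 24, 1.021 |
| 10% | 18, 1.054 | 23, 1.043 |
| 14.3% | 17, 1.085 | 21, 1.091 |
| 20% | 16, 1.118 | 20, 1.118 |

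The standard error is thus about 2 to 12% larger.

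**5. Selective loss of recoveries, on the mITT reading only (illustrative).**
- One low recovery among 20 treated, with that participant leaving early: 1/20 = 5.0% (0.1 to 24.9%) becomes 0/19 = 0% (0 to 17.6%).
- Two among 25: 2/25 = 8.0% (1.0 to 26.0%) becomes 0/23 = 0% (0 to 14.8%).
- Let the other recoveries have relative mean 1.00 and SD 0.20 (assumed). One low value of 0.25 to 0.50 among 20 gives a mean of (19 × 1 + 0.25)/20 = 0.963 to (19 × 1 + 0.50)/20 = 0.975, and an SD of 0.257 to 0.224. The mITT would show 1.00 and 0.20.

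**6. What changing the set would not restore.** SAP 4.1.1.5 flags a recovery as invalid when the post-infusion value is below the LLOQ or below the pre-infusion value, and drops it from the summary tables. This acts in any analysis set, so the lowest values would be absent from the safety set summary too.

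**The case against.** The case against rests on five arguments.

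- **The protocol sentence cannot be meant literally.** Protocol 9.4.4 puts safety analyses on the Safety Population, and PK is a subsection of it. Incremental recovery is not in the endpoint tables, and protocol 9.4.3 leaves the other exploratory endpoints to the SAP. This stands for recovery: its exclusion is not established, only that its set is unclear. It does not help the theoretical scores, which are a listed endpoint, or the risk score table, which the SAP assigns explicitly.
- **Early leavers remain visible.** A reader might infer that their scores are never tabulated, or that differential dropout by risk group would be hidden. The documents do not support that. SAP 4.6.1 presents assigned risk score frequencies, analysis sets, and disposition with reasons by assigned risk score, all for enrolled participants. What is missing is the component-level breakdown.
- **Low recoveries remain visible.** A reader might also infer that they vanish from all reporting. Loss of efficacy is an AESI (protocol 8.4.7), summarised on the safety set, and SAP 4.1.1.5 and 4.4.3 plan listings of FVIII levels and a count of samples failing validity. The gap is confined to the summary statistics.
- **Recovery is not always a Day 1 value.** Protocol 8.5.1 adds "If a participant is actively bleeding, the samples for incremental recovery will be postponed", and levels judged inappropriate may be repeated at Visit 5 or 6. This stands, but these are exceptions to the planned timing.
- **Using one set keeps the theoretical scores comparable with the primary outcome.** That is a fair reason to show the mITT as well. It is no reason to leave out treated participants when asking whether allocation would have changed, since outcome plays no part in that question.

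**Conclusion.** The point holds in a limited form. For the risk score component table, the SAP restricts to the mITT what the protocol promises on both sets, and declares no change. For the theoretical ABO/BMI scores, the mITT is the literal default, without an analytical reason. For incremental recovery the set is conflicting. Only on the mITT reading would low but valid recoveries be removed by later discontinuation.

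The size is modest and assumed: standard errors about 2 to 12% larger for 5 to 20% early loss. The selective effect on recovery may be complete for the affected cases, but its frequency is unknown. The loss-of-efficacy reports described in protocol 8.4.7 were in children under 6, whereas this trial enrols from age 12. It would therefore be wrong to say that the lower tail of recovery is cut off by the 4-month condition: whether that condition applies is unsettled, and the validity rule removes the most extreme values anyway. These are exploratory and baseline summaries, and the primary result is unaffected. The correction is small but worth making because it is free.

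**What to change.** - **Protocol 9.4.1:** limit the mITT sentence to the ABR, frequency of administration and the other effectiveness endpoints.
- **SAP 4.4.1 and 4.4.3:** analyse the theoretical scores, incremental recovery and Day 1 FVIII levels in all treated participants with the measurement, showing n.
- **SAP 4.4.2:** analyse the WAPPS-Hemo parameters in all treated participants with a result, showing n. This analysis is run at Month 3, before the 4-month cut.
- **SAP 4.6.2:** present the risk score table on both the safety and mITT sets, as protocol 9.4.5.2 states.
- **SAP 4.4.3:** within the planned count of samples failing validity, show separately the recoveries excluded because the post-infusion value was below the LLOQ or below the pre-infusion value, since changing the set does not bring them back.

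The cost is a wording change and a few extra table columns. No new data or procedures are needed.
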